### 10.4.2 Local laboratory values

Box plots of local laboratory values will be generated for baseline values and for values measured during the course of the study by treatment arm and visit. Each box plot will show the first quartile, the median, and the third quartile. Outliers (values outside the box plot) will also be plotted. If appropriate, horizontal lines representing boundaries for abnormal values will be plotted.

For each local laboratory measure, summary statistics will be presented by treatment arm and timepoint, as well as changes from baseline for postenrollment values. In addition, the number (percentage) of participants with local laboratory values recorded as meeting Grade 2 AE criteria or above as specified in the Division of AIDS Table for Grading the Severity of Adult and Pediatric Adverse Events will be tabulated by treatment arm for each timepoint after initiation of treatment interruption. Reportable clinical laboratory abnormalities without an associated clinical diagnosis will also be included in the tabulation of AEs described above.

### 10.4.3 Reasons for discontinuation of ATI and early study termination

The number and percentage of participants who discontinue ATI and who terminate the study early will be tabulated by reason and treatment arm.

### 10.5 Secondary analyses of immune responses and reservoir measurement

Analyses of immune responses and reservoir measurements will be descriptive using appropriate plotting techniques for describing measurements at a fixed time point (eg, boxplots and barplots) or longitudinally (eg, spaghetti plots) separately by treatment group. In addition, if enough samples are assayed we plan to do inferential and descriptive analyses as described in the following sections.

# 10.5.1 Evaluate the difference in anti-HIV immune responses or reservoir size between VRC01 and placebo recipient

TMLE will be used to estimate mean endpoints in each of the infected VRC01 and infected placebo groups, as well as the mean difference, all with 95% confidence intervals and associated 2-sided p-values, where the TMLE controls for all baseline covariates thought to potentially predict both HIV-1 infection and one of the secondary endpoints under study. This is needed for controlling for potential postrandomization selection bias given that analyzed treatment groups are selected postrandomization.

# 10.5.2 Assess whether anti-HIV immune responses or reservoir size are associated with time to meeting ART re-initiation criteria

Cox regression will be used to estimate cumulative incidence over time for groups defined by levels of immune response or reservoir size for each treatment group

### 11 SAFETY TABLES, PARTICIPANT LISTINGS, AND FIGURES

Approximately 6 months after enrollment of the first participant or after the 10th participant has completed 12 weeks of ATI (whichever comes first), an interim review of the study will occur. The Data Safety Monitoring Board (DSMB) will review accrual; retention; AE summaries, including all reported AEs ≥ Grade 3 and all STIs; summaries of the time to meeting ART reinitiation criteria; and longitudinal summaries of HIV-1 RNA and CD4+ T-cell count. Subsequent DSMB reviews will occur at least annually while participants remain on study. A DSMB may also be convened if a reason is identified by the DAIDS MO, study Co-chairs, or study statisticians in consultation with the HVTN 804/HPTN 095 Protocol Team leadership.

The following tables and figures will be presented to the DSMB and or FSR for safety.

### 11.1 List of Tables and Listings

The following tables are included in the DSMB reports and FSR for Safety:

- Enrollment by study site
- Baseline participant characteristics
- Study status and reasons for early termination
- Visit retention, Schedule 1
- Visit retention, Schedule 2
- Visit retention, Schedule 3
- Reasons for meeting ART re-initiation criteria
- Summary of time to meeting ART re-initiation criteria
- Turnaround times for ART Re-Initiation
- SAE listing
- STI listing
- Grade 1-5 Adverse Events by System Organ Class, Ordered by Decreasing Frequency
- Grade 3+ Adverse Events by System Organ Class, High Level Term, and Severity
- Grade 1-5 Adverse Events Related to ATI by System Organ Class, High Level Term, and Severity

Additional tables include in the FSR for Safety:

- Local Lab Value Summary Statistics
- Local Laboratory Values Meeting Grade 2 AE Criteria or Above

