### 5 SAFETY/VIROLOGIC(?) OBJECTIVES AND ENDPOINTS

Primary objective 1

• To evaluate the effect of VRC01 received in the immediate pre-HIV acquisition period and/or during early infection on the time to meeting ART re-initiation criteria in participants undergoing ATI

Primary endpoint 1

- Time to meeting criteria for ART re-initiation
- Frequency of sustained post-treatment HIV control, defined as  $\geq$  24 weeks off ART without meeting ART re-initiation criteria

Primary objective 2

• To evaluate the safety of ATI among HVTN 804/HPTN 095 participants

Primary endpoint 2

• Laboratory measures of safety, adverse events (AEs), SAEs (serious AEs), and rates of discontinuation

Secondary objective 2

• To evaluate the effect of VRC01 received in the immediate pre-HIV acquisition period and/or during early infection on viral load in participants undergoing ATI

Secondary endpoint 2

• Cumulative incidence of participants with viral load  $\geq$  200 at weeks 8, 16, and 24

Secondary objective 3

• To evaluate the effect of VRC01 received in the immediate pre-HIV acquisition period and/or during early infection on HIV reservoir size before and after ATI, and whether HIV reservoir measurements are associated with time to meeting criteria for ART reinitiation in participants undergoing ATI

Secondary endpoint 3

• Frequency of CD4+ T cells carrying intact and/or total pro-viral HIV DNA, replication competent virus, and/or cell-associated HIV RNA

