### 11.2 List of Figures

These graphs are included in the DSMB reports and FSR for Safety:

- Longitudinal Summaries of HIV-1 RNA Viral Load and CD4+ T-Cell Count (participant level) – all participants
- Longitudinal Summaries of HIV-1 RNA Viral Load and CD4+ T-Cell Count, restricted to participants who entered schedule 2 and to schedule 1 and 2 data points
- Cumulative Incidence of Meeting ART Re-Initiation Criteria
- Survival Plot of Time to Viral Load ≥ 200 (copies/ml)

Additional graphs included in FSR for Safety:

• Boxplots for local laboratory value (ALT, Direct Bilirubin, eGFR, Hemoglobin, Platelets, Absolute Neutrophil Count) at schedule 1 (visit 4, 8, 12, 14, 16, 18, 20, 21, 22, 23, 25, 27), schedule 2 (visit 40, 44, 48, 50, 52, 54, 56, 58, 60, 62, 64, 66), and schedule 3 (82, 84, 86, 89, 91)

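### Local hematology and chemistry values belong to primary endpoint 2, but their value-level displays are listed for the final report only; the DSMB sees these analytes only as reportable adverse events

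*SAP*

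**What the plan says.** Section 5 defines primary endpoint 2 as "Laboratory measures of safety, adverse events (AEs), SAEs (serious AEs), and rates of discontinuation".

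Under the primary safety analysis, section 10.4.2 plans three displays of local laboratory values:
- boxplots by arm and visit;
- summary statistics by arm and timepoint, with changes from baseline;
- counts of participants with values at Grade 2 or above, by arm, at each timepoint after ATI begins.

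It also links these values to the AE tables: "Reportable clinical laboratory abnormalities without an associated clinical diagnosis will also be included in the tabulation of AEs described above".

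Section 11 sets out what the board examines: "The Data Safety Monitoring Board (DSMB) will review accrual; retention; AE summaries", then summaries of time to meeting the ART re-initiation criteria, "and longitudinal summaries of HIV-1 RNA and CD4+ T-cell count". Hematology and chemistry are not named.

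Sections 11.1 and 11.2 sort the outputs into two groups, those for both DSMB reports and the Final Study Report (FSR) and those for the FSR alone. The shared group includes "Grade 1-5 Adverse Events by System Organ Class, Ordered by Decreasing Frequency" and "Longitudinal Summaries of HIV-1 RNA Viral Load and CD4+ T-Cell Count (participant level". The two local laboratory tables stand under "Additional tables include in the FSR for Safety", and the boxplots stand under "Additional graphs included in FSR for Safety".

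**The concern.** The stated aim of the safety evaluation (section 9) is to find safety concerns associated with ATI, and local laboratory measures are a named part of the endpoint that serves it. The displays of recorded values, including the one tied to timepoints after ATI starts, are scheduled only for the end of the study. Section 3 expects most participants to stay 13 to 18 months and some up to about 2½ to 3 years. Section 11 plans a first review at about 6 months, or once the 10th participant has completed 12 weeks of ATI if that is sooner, and then at least one review a year. As the lists stand, none of those reviews includes a display of recorded hematology or chemistry values.

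What is at stake is how early a shift in, say, platelets, neutrophils or ALT during ATI becomes visible to the DSMB when it has not been recorded as AEs. The question falls within this document, because section 2 says the SAP governs the safety analysis for both DSMB reports and the FSR.

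**Working it through.** No formula applies. The check compares the endpoint, the planned analysis and the two output lists item by item.

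| Display planned in SAP 10.4 or listed in 11.2 | DSMB reports | FSR |
|---|---|---|
| AE tables, Grade 1-5 and Grade 3+ (11.1) | yes | yes |
| SAE listing, STI listing (11.1) | yes | yes |
| Early termination, reasons for meeting re-initiation criteria (11.1) | yes | yes |
| HIV-1 RNA and CD4+ plots, time to viral load ≥ 200 (11.2) | yes | yes |
| Local laboratory summary statistics (11.1) | no | yes |
| Local laboratory values at Grade 2 or above (11.1) | no | yes |
| Local laboratory boxplots (11.2) | no | yes |

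**Step 1, coverage.** All three local laboratory displays are FSR-only. The boxplots cover six analytes: ALT, direct bilirubin, eGFR, hemoglobin, platelets and absolute neutrophil count. Section 11.2 lists 12 visit codes for Schedule 1 and 12 for Schedule 2, so 12 + 12 = 24 visit codes during ATI. This counts displays; it does not measure missed safety signals.

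**Step 2, data availability.** The schema in Appendix I is partly broken in the extracted text. Its legible ATI cells show hematology and chemistry drawn every 4 or 8 weeks, so values would exist at each DSMB data cut.

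**Step 3, what the AE route carries.** Section 10.4.2 sends an abnormality without a clinical diagnosis into the AE tables only if it is reportable. Sections 10.4.1 and 11.1 organize those tables by System Organ Class, preferred or high level term, and severity or relationship to ATI. Each participant is counted once per category, at the maximum severity or strongest relationship. The tables do show treatment arm. They do not show timepoint, change from baseline, or values that were not reported.

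**Step 4, what the missing table would add.** This depends on the reporting threshold, which the SAP does not define. Two bounding assumptions:
- If every value at Grade 2 or above is reportable, the table adds only arrangement by analyte and timepoint.
- If only higher grades or selected abnormalities are reportable, it also adds recorded Grade 2 or above values that the DSMB would otherwise not see.

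Under either assumption, drift below Grade 2 would appear only in the summary statistics and boxplots.

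**The case against.** The strongest reply is that the DSMB already has the laboratory data most relevant to ATI. Participant-level viral load and CD4+ counts are in its package, and the primary hypothesis in section 4.1 concerns suppression of viremia and maintenance of CD4+ counts. Reportable hematology and chemistry abnormalities reach it through AE tables covering all grades, and section 11 allows a board to be convened outside the schedule. The output lists also agree with the review items in section 11, so nothing is misstated. The version history records that extra analyses were added for the FSR, which fits a deliberate choice. All of this stands, and it limits the point to a suggestion about reporting content.

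Three stronger readings are tempting, and the document does not support them:
- A reader might infer that the DSMB monitors ATI without laboratory results. The HIV-1 RNA and CD4+ plots and the AE route show otherwise.
- A reader might infer that unreported values reach nobody at group level during ATI, or that a hematology or liver signal could not lead the DSMB to act. Reporting rules and any other ongoing safety review may be in the protocol, which is not at hand, and a reportable abnormality does reach the board.
- A reader might take Table 4-2 as a measure of the gap. It gives the chance of observing SAEs. The DSMB does not rely on SAEs alone, and adding laboratory displays would not change those figures.

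The reply does not cover recorded values that are not reportable, or any view of these analytes by timepoint.

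**Conclusion.** The point holds in a limited form. The value-level displays of local hematology and chemistry, part of a primary safety endpoint, are planned for the FSR only: two of two tables and the one set of boxplots. In DSMB reports these analytes appear only through AE reporting. The omission itself follows directly from sections 11, 11.1 and 11.2. Its practical size cannot be determined from the SAP, because it depends on which abnormalities are reportable. It ranges from a loss of timepoint detail and sub-Grade 2 drift to the additional absence of some Grade 2 or above values. AEs, SAEs and early termination, which also bear on primary endpoint 2, do reach the DSMB, so review of that endpoint as a whole is not deferred. This is a cheap improvement, not an error that must be corrected.

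**What to change.** In section 11.1, move the table of local laboratory values at Grade 2 or above from the FSR-only list to the list shared by DSMB reports and FSR. In section 11, add local laboratory values to the items the DSMB reviews, so that the text and the lists still agree.

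Moving the boxplots as well is optional. The first review may come when only about 10 participants have completed 12 weeks of ATI, or fewer if the 6-month trigger comes first, and boxes split by arm and visit would then rest on very few values.

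The Grade 2 or above table is already specified in section 10.4.2, so the change needs no new data, endpoint or method, only a run of that table at each DSMB data cut. The downside is a slightly longer DSMB report.

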### 11.2 List of Figures

These graphs are included in the DSMB reports and FSR for Safety:

- Longitudinal Summaries of HIV-1 RNA Viral Load and CD4+ T-Cell Count (participant level) – all participants
- Longitudinal Summaries of HIV-1 RNA Viral Load and CD4+ T-Cell Count, restricted to participants who entered schedule 2 and to schedule 1 and 2 data points
- Cumulative Incidence of Meeting ART Re-Initiation Criteria
- Survival Plot of Time to Viral Load ≥ 200 (copies/ml)

Additional graphs included in FSR for Safety:

• Boxplots for local laboratory value (ALT, Direct Bilirubin, eGFR, Hemoglobin, Platelets, Absolute Neutrophil Count) at schedule 1 (visit 4, 8, 12, 14, 16, 18, 20, 21, 22, 23, 25, 27), schedule 2 (visit 40, 44, 48, 50, 52, 54, 56, 58, 60, 62, 64, 66), and schedule 3 (82, 84, 86, 89, 91)

# Appendix I: Schema

SCHEDULE 3	FOLLOW UP FOLLOW UP ON ART ON ART WEEKS 12-28 WEEKS 40-52	Q4 WEEKS Q12 WEEKS	Q8 WEEKS Q12 WEEKS	Q12 WEEKS Q12 WEEKS
S	FOLLOW UP ON ART WEEKS 0-12	Q2 WEEKS	Q4 WEEKS	Q4 WEEKS
	PRE- REINITIATE ART	>	>	ı
	ATI + Viremia WEEKS 40-52 	Q4 WEEKS	QB WEEKS	QB WEEKS
SCHEDULE 2	ATI+Viremia WEEKS 10-36	Q2 WEEKS 	Q4 WEEKS*	EEKS
	ATI+Viremia WEEKS 0-8	WEEKLY	Q2 WEEKS	Q4 WEEKS
	ATI WEEKS 28-52 	Q4 WEEKS	Q8 WEEKS	Q8 WEEKS
CHEDULE 1	ATI WEEKS 10-24	Q2 WEEKS	Q4 WEEKS	EEKS
S	ATI WEEKS 0-8	WEEKLY	Q2 WEEKS	W #5
Ī	PRE. DISCONTINUE ART	N	٨	*
	SCREEN	٨	>	٨
		Plasma HIV RNA	CD4+& CD8+ T cell counts	Hematology & Chemistries

. QUARTERLY FOLLOW-UP VISITS MAY CONTINUE BEYOND WEEK 5.2 FOR PARTICIPANTS WHO DO NOT MEET CRITERIA FOR TRANSITION TO SCHEDULE 2.

Page 14 of 14

 QUARTERLY FOLLOW-UP VISITS MAY CONTINUE BEYOND WEEK 5.2 FOR PARTICIPANTS WHO DO NOT MEET CRITERIA FOR ART RE-INITIATION.
3 OR WEEKLY FOR WEEKS 10-24, IF VL ≥ 200 copies/ml.

OR Q2 WEEKS FOR WEEKS 10-24 IF VL ≥ 200 copies/mL
